5.5. Institutional guidelines for whole breast irradiation treatment planning

5.5.1. Whole breast RT target volumes

5.5.1.1. Gross Tumor Volume (GTV)

No GTV

5.5.1.2. Clinical Target Volume (CTV)

- Tumor bed is delineated by identifying post-operative seroma and associated surgical clips + 5 mm
- Whole breast PTV will be determined following the tangents placed/finalized by the treating physician, by subtracting 5 mm from the block edge, skin and the lung/rib/intercostal muscle interface. See Figure 4.
- Tumor bed coverage in the whole breast radiation: The tumor bed CTV is expanded by 15 mm in all directions (anatomically constrained by skin and not the chest wall). The block edge of the tangent will be at least 15 mm to ensure dose coverage of the tumor bed CTV

[figure not shown]

Figure 4. Steps to generate whole breast PTV (A)The purple line represents the 50% isodose line which is used to create volume. (B) The red line represents the 50% volume subtracting 5 mm from the skin and 1 cm superiorly and inferiorly.(C) The blue line subtracts the lung + 5 mm.

5.5.2. Dose prescription

The dose delivered to the whole breast PTV for patients in the study will be 50 Gy in 25 fractions OR 40 Gy in 15 fractions with the dose prescribed to the ICRU reference point.

5.5.3. Treatment delivery technique

- 3-D conformal RT with control points is the standard (40), with the maximum of 4 control points.
- Hybrid inverse planned IMRT will be attempted(41), if:
 - Whole breast V105 >75 cc in conventional fractionated plan or V105 > 50 cc in hypofractionated 3D plan
 - Whole breast Dmax > 110%
 - 95% of the Tumor bed PTV cannot be covered by 95% of the prescription dose
 - 95% of the Tumor bed CTV cannot be covered by 95% of prescription dose
- Hybrid plan will be used in preference to 3D conformal RT with control points, if hot spots are decreased by 20% as measured by the absolute volume of V105 (i.e. if V105 in forward plan is 100 cc, hybrid plan has to reduce to 80 cc or less) as they decrease fibrosis and acute skin toxicity (41-43) or coverage is improved by 20%

5.5.4. Dose-volume analysis for the whole breast

- 95% of the Whole breast PTV receives >95% of prescribed dose
- 95% of the Tumor bed CTV receives > 95% prescribed dose
- 95% of the Tumor bed PTV receives > 95% prescribed dose

5.5.5. Dose-volume analysis for normal structures

- Normal structures(22), unfortunately there is no clear DVH criteria that predicts increased side effects – values chosen were arbitrary based on clinical practice
- Ipsilateral lung: V20 < 20%
- Heart: V30 < 5%, mean heart dose < 5Gy

5.5.6. Timing

Treatment to the whole breast will begin within 7-8 days from the tumor bed boost (GammaPodTM) treatment unless an adverse event occurred from the GammaPod treatment.

6. Surgical Resection

- Lumpectomy and lymph node sampling or dissection should be performed according to institutional standard of care.
- Surgical clips to delineate the surgical bed is the standard of care of our referring surgeons.

7. Adjuvant Systemic Therapy

- Chemotherapy and/or hormonal therapy may be given pre-operatively or post-operatively according to standard of care and will be recorded.
- Hormonal therapy, if used, will be delivered concurrently and recorded.

8. Pathology

Pathology assessment of the lumpectomy and lymph node assessment will follow current standard of care.

9. Patient Assessments

9.1. Study parameters

Assessment	Pre-Entry	During Radiation	At 6 weeks ^e	At 6 months ^e	At 1 year ^e
H&P, Breast Exam	X		X	X	X ^d
Weight	X			X	X ^d
Bra cup size	X			X	X
Disease status	X		X	X	X ^d
Mammograms	X			X ^f	X ^c
Toxicity		X ^b	X ^b	X ^b	X ^b
Photographs	X ^a	X ^a		X ^a	X ^a

a. Photographs will be obtained prior to GammaPod treatment, following the removal of the breast immobilization device after the treatment is delivered, on the day whole breast radiation starts and on the last day of treatment as well as at their 6 and 12 month follow up.

b. Patients will be seen on day of GammaPod treatment and following GammaPod treatment on day of 1st whole breast treatment, then weekly during whole breast radiation and all toxicity will be recorded at each of the time points or more often as clinically indicated.

c. Yearly thereafter

d. Clinical examination and disease status assessment at 6-month intervals for the first 3 years, and yearly thereafter

e. Time points are from the start of radiation therapy

f. Mammogram 6 months after radiation therapy, then yearly thereafter.

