1.3. Schema/procedure

The general treatment sequence is shown in the flow chart below. After lumpectomy and sentinel node biopsy, the patient may or may not be recommended for adjuvant chemotherapy. If chemotherapy is recommended, radiation therapy will start within 6-8 weeks from completion of chemotherapy. If chemotherapy is not recommended or performed prior to surgery, radiation therapy will start within 6-8 weeks following surgery. Rather than delivering the tumor bed boost at the end of the whole breast radiation, we will deliver the tumor bed boost dose of 8 Gy in a single treatment using the GammaPod before whole breast radiation. The clinical target volume for the single treatment is the tumor bed (defined as the surgical cavity including surgical clips and any surgical changes) plus a 5 mm uniform margin. A further 5 mm uniform expansion in all directions will be added to the clinical target volume to make the planning target volume. This 5 mm margin is based on our setup reproducibility study with the current patient loader and breast cup system (GCC1047), as well as conservatively taking into account mechanical uncertainty of couch positioning. Twelve patients have contributed data to the setup reproducibility analysis (see the Pre-Clinical Tests section, Tab 3). The reproducibility of target location within the cup to within two standard deviations of the mean (95% confidence limit) has been found to be 2.9 mm.

After the single fraction GammaPod treatment, standard whole breast radiation therapy delivering 50 Gy in 25 treatments or 40 Gy in 15 treatments will be administered.

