At the conclusion of the treatment, the patients will be asked about the comfort of the cup system and procedure, and their skin will be checked for any signs of irritation from the breast immobilization system or the use of the medical adhesive spray during radiation treatment. The cup and flange will also be visually checked for any apparent effects.

At the time of conventional radiotherapy simulation, it will be determined whether or not the patient is an eligible candidate for GammaPod boost treatment. Whether or not the patient receives GammaPod treatment, her whole breast irradiation will start up to 7-8 days after the day of conventional radiotherapy simulation. This time is needed for physician contours, treatment planning by our dosimetry team, physician plan approval and physics plan approval (typically 4 working days) and also allowing for standard practice of beginning a course of whole breast irradiation on a Monday. This timeline is purely a function of workflow rather than clinical/radiobiological considerations. The CT images acquired with the patient in the supine position during simulation will be used for treatment planning. Whole breast treatments are devised according to our departmental guidelines. GammaPod patients will return on a single day prior to their conventional treatment to be CT scanned in the prone orientation and treated with GammaPod. It is possible that GammaPod simulation and treatment will be on the same day as conventional radiotherapy simulation, depending on schedules and patient availability. The timing of GammaPod boost treatment relative to conventional radiotherapy whole breast treatment does not affect the whole breast radiotherapy dose prescription. This is consistent with current clinical practice concerning boost dose delivery, whether pre (i.e. intraoperative radiotherapy) or post (i.e. external beam radiotherapy or brachytherapy) whole breast radiotherapy. Beginning on the day of GammaPod treatment, patients will be evaluated weekly for acute toxicities, as is our clinic's standard practice.

2. Objectives

The primary study objective is to demonstrate the feasibility and safety of delivering a tumor bed boost dose using the GammaPod™ stereotactic system for patients undergoing breast conserving therapy. Efficacy is not among the objectives of this study.

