2.1.2. Secondary Endpoints

- The evaluation of overall patient comfort in the GammaPodTM procedure.
- The evaluation of acute toxicity during and up to 1 month after GammaPodTM TB boost.
- The evaluation of long-term toxicity at one year to assess the presence of subcutaneous fibrosis, and fat necrosis.
- The evaluation of the use of Hollister Medical Adhesive spray for sealing the cup flange during radiation therapy and its effects, if any, on the patient's skin

3. Patient Selection Criteria:

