9.2. Adverse event reporting

9.2.1. Anticipated toxicities

- Fatigue is the anticipated systemic reaction to radiation treatment.
- Skin irritation, erythema and desquamation may also occur.
- Breast edema, tenderness, and myositis are potential acute side effects.
- Long-term complications may include radiation pneumonitis, rib fractures, cardiac complications, and wound healing complications. Although the additional risk from this single treatment should be minimal in comparison to the whole breast radiation.
- Patients will be seen on day of GammaPod treatment and following GammaPod treatment on day of 1st whole breast treatment, then weekly during whole breast radiation and side effects will be recorded at each of the time points.

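### No CTCAE grade is scheduled before the cup and boost, and no separate acute toxicity summary is planned up to the first whole breast fraction

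*Combined protocol and SAP*

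**What the plan says.** **Schedule.** The Section 9.1 table has five time columns, starting with Pre-Entry. Its toxicity row reads "Toxicity X ^b X ^b X ^b X ^b": four marks, none under Pre-Entry. Footnote b explains them: "Patients will be seen on day of GammaPod treatment and following GammaPod treatment on day of 1st whole breast treatment". Visits are then every week for the rest of the whole breast course. On what is captured at these visits, the footnote says: "all toxicity will be recorded at each of the time points or more often as clinically indicated". Section 1.3 agrees: "Beginning on the day of GammaPod treatment, patients will be evaluated weekly for acute toxicities". It places the skin and comfort check at the end of the procedure.

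**Baseline material that is planned.** Section 9.1 has a history, physical and breast exam at Pre-Entry. Photographs are taken before the boost, after the cup comes off, and on the day whole breast radiation starts.

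**State of the patients at entry.** All have had a partial mastectomy. Without postoperative chemotherapy, "radiation therapy will start within 6-8 weeks following surgery"; with it, radiation starts 6-8 weeks after chemotherapy ends (Section 1.3). Section 9.2.1 anticipates fatigue and skin reactions, and adds "Breast edema, tenderness, and myositis are potential acute side effects".

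**Acute window.** Section 2.1.2 plans "The evaluation of acute toxicity during and up to 1 month after" the boost. Section 10.1 first takes acute to mean within a month of protocol therapy, and later defends an endpoint one month after whole breast radiation.

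**Gap between treatments.** Section 5.5.6: "Treatment to the whole breast will begin within 7-8 days from the tumor bed boost", unless the GammaPod treatment has caused an adverse event.

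**The concern.** This is a single-arm, first-in-human device study whose stated objective is feasibility and safety. With no comparator, each patient's own condition before the procedure is the main reference for judging what the cup, adhesive and boost did.

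Surgery or chemotherapy could plausibly leave fatigue, edema, tenderness or induration at entry, and whole breast radiation can produce several of the same findings soon afterwards. Without a graded baseline and a cut at the first whole breast fraction, the acute toxicity table would blend up to four sources. A mild device effect could be lost in the whole breast reactions, or a surgical residue charged to the device. A baseline grade that was never taken cannot be reliably reconstructed later.

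**Working it through.** **1. What is graded, and when.**

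| Time | Planned | CTCAE grade scheduled? |
|---|---|---|
| Pre-Entry | History, physical, breast exam, photographs | No |
| Boost day | Photographs before and after; skin and comfort check afterwards; toxicity recorded | Yes, but not stated to precede cup fitting |
| First whole breast day | Toxicity recorded; photographs | Yes, but not stated to precede the fraction |
| Weekly during whole breast radiation | Toxicity recorded | Yes |

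The time points for a split exist. The baseline grade, the order of events on the first whole breast day, and any planned use of that day as a cut do not.

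**2. Overlap under Section 2.1.2.** Inputs: gap g = 7 or 8 days (Section 5.5.6); window W = 30 days (one month taken as 30 days, an assumption). Share after whole breast radiation has started = (W − g)/W.

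- g = 7: 23/30 = 76.7%
- g = 8: 22/30 = 73.3%

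**3. Overlap under the later wording in Section 10.1.** Inputs: 15 or 25 fractions (Section 5.5.2). I assume five fractions a week and a Monday start, so the last fraction falls 18 or 32 days after the first. Window end = g + course + 30, in days from the boost. Share = (end − g)/end.

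| Gap | Fractions | Last fraction, day | Window end, day | Share after whole breast start |
|---|---|---|---|---|
| 7 | 15 | 25 | 55 | 48/55 = 87.3% |
| 8 | 15 | 26 | 56 | 48/56 = 85.7% |
| 7 | 25 | 39 | 69 | 62/69 = 89.9% |
| 8 | 25 | 40 | 70 | 62/70 = 88.6% |

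**4. How far the windows disagree.** The window in Section 2.1.2 closes at day 30, and the later one in Section 10.1 at day 55-56 or 69-70: a difference of 25-26 or 39-40 days. With 25 fractions, the Section 2.1.2 window closes 9-10 days before the last fraction (39 − 30, 40 − 30).

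**5. Can a cup effect outlast the gap?** Section 1.2 reports one patient in the earlier cup studies whose blisters took two weeks to resolve. A reaction of that length would extend 6-7 days into whole breast radiation (14 − 8, 14 − 7). The investigators linked it to surgical volume loss and to fibrosis from prior radiation. Prior radiation is excluded here; surgical volume loss is not.

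**6. Design figures.** The Simon design (stop at 5 or fewer of 8, reject at 13 or fewer of 17, 60% versus 90%) is sized on dose distribution. The exact binomial calculation gives type I error 0.0436 (stated 4.4%), power 0.9045 (90.5%), early termination 0.685 (68%) and expected size 8 + 9 × (1 − 0.685) = 10.84 (10.8). All reproduce, and none depends on toxicity.

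**The case against.** A reader might infer that the acute endpoint cannot show what the GammaPod procedure caused. The documents do not support that.

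- Toxicity is recorded on the boost day and again on the first whole breast day, so a split can be made from the data. Only its tabulation is unplanned.
- Photographs before the boost and after cup removal bracket the procedure.
- Comfort and adhesive skin effects are separate secondary endpoints, checked before any whole breast radiation, so immediate effects are not confounded by it. Section 11 adds a suspension rule for complaints about the cup or setup.
- Section 10.1 counts serious device-related events, and Section 5.5.6 presupposes a judgement on whether an adverse event came from the GammaPod treatment.
- Acute toxicity is secondary, and Section 10.1 leaves late toxicity out of the statistical evaluation.

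Two further inferences go too far. One is that a pre-existing finding will be counted as acute toxicity. The plan is silent: Section 10.1 speaks of toxicities occurring within the window and Section 9.2.2 of radiation effects, which point to onset or cause. The other is that whole breast radiation starts the day after the boost, making the overlap 29/30, or 97%. Section 1.3 says only that the boost falls on some earlier day; a one-day gap is not excluded, but it is an assumption.

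What the objection leaves unanswered is narrower. Photographs cannot grade fatigue, tenderness or induration, and the pre-entry exam carries no grade. No rule assigns non-serious toxicity to the device. Section 10.1 argues that because the cup precedes whole breast radiation, the long window is suitable; that ordering is better used to justify a separate early summary.

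**Conclusion.** The point holds in a limited form. No graded baseline precedes the cup and boost, events are not defined relative to baseline, no summary up to the first whole breast fraction is planned, and the acute window has inconsistent ends. Non-serious boost effects and later skin reactions are therefore hard to attribute; immediate cup and adhesive effects are better protected.

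The overlap is 73-77% of the window in Section 2.1.2, or 86-90% if the window ends one month after whole breast radiation. Both ranges rest on the stated 7-8 day gap and a 30-day month; the second also assumes five fractions a week from a Monday. A shorter gap would raise them. The documents give no prevalence of residual symptoms at entry, so the number of patients affected cannot be stated. The primary analysis and sample size are untouched. This is an inexpensive improvement, best made before enrolment.

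**What to change.** 1. Section 9.1: add a Toxicity mark at Pre-Entry. At the exam already scheduled there, grade the Section 9.2.1 items plus induration/fibrosis by CTCAE v4.0.
2. Sections 2.1.2 and 10.1: count an acute event only if it is new or worse than the pre-entry grade.
3. Section 9.1, footnotes a and b: state that the grading and photograph on the first whole breast day precede the first fraction.
4. Sections 2.1.2 and 10.1: reconcile to one acute window.
5. Section 10.1: tabulate acute toxicity separately (a) from the boost to the first whole breast fraction and (b) from that fraction to the end of the window, among patients who received the boost. Section 10.2 sends patients with unacceptable plans to a conventional boost, so this denominator may be below 17.

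The cost is one extra form at an existing visit and one extra table, with no added patients or visits. The limitation is that summary (a) covers about a week per patient at the stated gap, so it captures early effects only and should be described that way.

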9.2. Adverse event reporting

9.2.1. Anticipated toxicities

- Fatigue is the anticipated systemic reaction to radiation treatment.
- Skin irritation, erythema and desquamation may also occur.
- Breast edema, tenderness, and myositis are potential acute side effects.
- Long-term complications may include radiation pneumonitis, rib fractures, cardiac complications, and wound healing complications. Although the additional risk from this single treatment should be minimal in comparison to the whole breast radiation.
- Patients will be seen on day of GammaPod treatment and following GammaPod treatment on day of 1st whole breast treatment, then weekly during whole breast radiation and side effects will be recorded at each of the time points.

9.2.2. Toxicity reporting

Acute radiation effects will be evaluated and scored using the NCI CTCAE v. 4.0. A copy of the CTC version can be downloaded from the CTEP homepage (<http://ctep.info.nih.gov>). Please note that this study will not be using separate toxicity scales for acute and late radiation effects. All acute effects and late effects that occur within one year will be recorded in ONCORE. Data and safety monitoring will be reported to the in-house data safety monitoring board bi-annually.

9.2.3. Photographs to evaluate toxicity

- Digital images of the breast will be taken prior to GammaPod treatment, following the removal of the breast immobilization device after the treatment is delivered, on the day whole breast radiation starts and on the last day of treatment as well as at their 6 and 12 month follow up.
- All images will exclude the patient's face.
- The first image will be a close up of the ipsilateral breast undergoing planned therapy in a straight frontal view with both arms elevated above the patient's head.
- The second image will be a close up of the ipsilateral breast undergoing planned therapy in a straight frontal view with both hands on the patient's hips.
- The third image will be a straight frontal view encompassing both the patient's breasts with the patient's hands on her hips.

9.2.4. Life-threatening and grade 4 events

All life-threatening events (events, which in view of the investigator, place the patient at immediate risk of death from the reaction) or Grade 4 events that are definitely, possibly, or probably related to protocol treatment using radiation therapy will be reported according to IRB reporting policy. Every Severe Adverse Event (SAE) will be reported on FDA 3500 A (MedWatch Form).

9.2.5. Fatal events (Grade 5)

All deaths with the attribution of definitely, possibly, or probably related to protocol radiation therapy must be reported according to IRB reporting policy. Every Severe Adverse Event (SAE) will be reported on FDA 3500 A (MedWatch Form). All deaths during and within 30 days of completion of protocol radiation therapy, regardless of attribution, must be reported according to IRB reporting policy. Every Severe Adverse Event (SAE) will be reported on FDA 3500 A (MedWatch Form)

<https://www.accessdata.fda.gov/scripts/medwatch/>

If the event is more than 30 days from completion of radiation treatment, but is felt to be definitely, possibly, or probably resulting from protocol radiation therapy, this event must be reported according to IRB reporting policy. Every Severe Adverse Event (SAE) will be reported on FDA 3500 A (MedWatch Form).

10. Statistical Considerations

10.1. Objectives

The primary objective is to demonstrate the feasibility and safety of delivering a tumor bed boost dose using the GammaPod stereotactic system for patients undergoing breast conserving therapy. Primary feasibility endpoints will include an estimate of reproducibility of the radiation technique. Reproducibility will be assessed on the basis of radiation therapy being scored as acceptable, marginally acceptable, or unacceptable using the criteria described in Section 5.4.3. The proportion of patients eligible for a GammaPod TB boost will be based on clinical and pathological findings. Secondary safety endpoints will include the number and type of serious adverse device-related events, the incidence of acute radiation. Acute toxicity will be assessed using the NCI CTCAE v4.0 criteria. Toxicities will be defined as acute if they occur within one month of protocol therapy. TB boost is not experimental. Delivering a single large dose to the TB is also not new. Based on previous intracavitary, intraoperative TB irradiations with 20 to 21 Gy(30, 44-46), we do not expect elevated significant late side effects. To reiterate, this study will treat only to 8 Gy as opposed to 20 to 21 Gy and is treating a similar volume as other intraoperative experiences where thousands of patients have been treated. Subsequently, the late toxicity profile will not be part of the statistical evaluation in this feasibility study. However, toxicity will be reviewed at 12 months after the completion of the radiation therapy and the data will be captured. Acute effects may be related to placement of the immobilization device but since it is placed prior to the whole breast radiation, the one month post whole breast radiation endpoint is appropriate.

